1.0 Objectives

1.1 Study Objectives

1. Determine if patients wearing a CAM (Controlled Ankle Movement) walker boot have a change in weight compared to patients who wear a CAM boot and are provided nutritional and upper body exercise (gender appropriate) information at the time the CAM boot is dispensed.
2. Determine, if weight is gained or lost, the average amount gained/lost over the treatment period.

1.2 Primary Study Endpoints

1. Weight gain (or loss) at time patient no longer is required to wear the CAM boot.

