2.2 Previous Data – N/A

2.3 Study Rationale

We hypothesize that participants who are provided nutritional and gender appropriate upper body exercise information, at time CAM boot is prescribed, will maintain their current weight or lose while in the CAM boot. We further hypothesize that participants without nutritional and gender appropriate upper body exercise will gain between 10-15 pounds on average.

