7.2.2 Visit 2 – Final Follow-Up Visit

Patients will return to the clinic site for their standard of care visit. At their final visit (when CAM boot use is no longer required), the following will occur:

- **Group 1 (Control):** Patient will be given an Albumin lab test request for blood (8mL) to be drawn at the PSHMC Clinical Laboratories at time of the final study visit. The blood draw

must occur within 5 days of the final visit. Final height and weight will be measured and recorded using a scale located in the practice site clinic.

- Group 2 (Intervention): Final height and weight will be measured and recorded using a scale located in the practice site clinic. Patient will be given an Albumin lab test request for blood (8mL) to be drawn at the PSHMC Clinical Laboratories at time of the final study visit. The blood draw must occur within 5 days of the final visit. Patient will complete the Participant Survey. The dietary scale is to be returned at this visit. Return of the Patient Diary is optional.

	Control	Intervention	
Visit 1 (Enrollment)	Albumin level (bloodwork)	Albumin level (bloodwork)	
	Weight	Weight	
	Height	Height	Patient Diary provided to patient
			Nutritional/Exercise Guidelines provided to patient
			Dietary Scale provided to patient
	Control	Intervention	
Visit 2 (Final Visit)	Albumin level (bloodwork)	Albumin level (bloodwork)	
	Weight	Weight	
	Height	Height	Participant Survey
			Dietary Scale returned
			Patient Diary returned (optional)

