7.3 Duration of Participation

Patients will be enrolled in the study from time the CAM boot is dispensed until they no longer need to wear the CAM boot. The patient will be seen a total of two times (enrollment and final follow-up visit).

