9.0 Statistical Plan

9.1 Sample size determination

Approximately 50 patients will take part in this research study – 25 patients will make up the intervention group (nutritional/exercise information) group and an additional 25 will make up the control group.

We expect the change in weight from baseline to of CAM boot removal + no nutritional information group to increase by 10 lbs. and to remain unchanged (i.e., 0 lbs.) in the CAM boot + nutritional information group. Further, we assume the standard deviation for the change in weight form baseline to time of CAM boot removal will be 12 lbs. Based on these assumptions, a sample size of 25 per group will provide 82% power to detect a difference in the change in weight between the two groups of 10 lbs. using a two-sided test having a significance level if 0.05.

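### Does comparing total pounds at boot removal, without using boot time, undermine the primary comparison?

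*Combined protocol and SAP*

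**What the plan says.** Section 1.2 defines the primary endpoint as "Weight gain (or loss) at time patient no longer is required to wear the CAM boot". Section 7.3 sets follow-up by the boot and not by the calendar: "Patients will be enrolled in the study from time the CAM boot is dispensed until they no longer need to wear the CAM boot". There are two visits, and section 7.2.2 ties the second to the same event: "At their final visit (when CAM boot use is no longer required), the following will occur". No number of weeks, minimum or maximum is given.

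Section 2.3 expects that "participants without nutritional and gender appropriate upper body exercise will gain between 10-15 pounds on average". Section 9.1 plans for a 10 lb gain in the control arm and for weight "to remain unchanged (i.e., 0 lbs.) in the CAM boot + nutritional information group". It assumes that "the standard deviation for the change in weight form baseline to time of CAM boot removal will be 12 lbs" and concludes that "a sample size of 25 per group will provide 82% power to detect a difference in the change in weight between the two groups of" the planned size (10 lb), two-sided at 0.05.

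Section 9.2 names a two-sample t-test, or Wilcoxon Mann Whitney if the data are not normal, with no covariate. Section 7.2 describes unblinded allocation by sealed envelope, and its visit table does not list boot time.

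**The concern.** If weight is gained while the boot is worn, a patient booted for a long time should gain more than one booted briefly, yet both enter the test as one figure in pounds. Any adult prescribed a boot in the practice can enroll, so boot times may vary widely. With 25 per arm, chance could give one arm more long-boot patients. The staff who decide when the boot comes off know the allocation, so timing could also drift by arm.

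Three things seem to be at stake: power lost to avoidable noise, a false difference if boot time is unequal, and a result in pounds that is hard to apply elsewhere because the period is not stated. The natural remedy would be to record expected boot time before randomization, add it to the primary model, and report pounds per week as support.

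**Working it through.** **Inputs from section 9.1:** 25 per arm, difference 10 lb, SD 12 lb (variance 144), two-sided 0.05. **Assumed, because the documents give no boot times:** control gain proportional to boot time with mean 10 lb, and a coefficient of variation (CV) of boot time, c, of 0.25 to 0.5.

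**1. The plan's own figure.** Noncentrality = 10 / (12 × √(2/25)) = 10 / 3.394 = 2.946 on 48 degrees of freedom. Noncentral t power is 82.3%, so the stated 82% reproduces.

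**2. Is the noise already counted?** Section 9.1 defines the 12 lb SD for change up to boot removal. On that wording, variation in boot time is part of the 12 lb and planned power is unaffected. Under the assumed model its share of the control-arm variance is (10c)²/144: 9/144 = 6.2% at c = 0.3 and 25/144 = 17.4% at c = 0.5.

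**3. Chance imbalance.** Suppose there is no treatment effect and both arms gain 10 lb on average. Chance differences in mean boot time then move the arm difference with SE 10c√(2/25): 0.71 lb at c = 0.25 and 1.41 lb at c = 0.5, or 95% limits of ±1.4 and ±2.8 lb. The whole difference has SE 3.394 lb, or limits of ±1.96 × 3.394 = ±6.7 lb. The boot-time part is a component of the error that the t-test already estimates. Simulation (100,000 trials per setting, gamma boot times, CV 0.25 to 0.75) gives type I error of 4.9-5.1%.

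**4. What could a covariate recover?** Removing all boot-time variance from the control arm lowers the pooled variance by (10c)²/2:

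| c | Pooled variance | Pooled SD | Power |
|---|---|---|---|
| 0.3 | 144 − 4.5 = 139.5 | 11.8 | 83.5% |
| 0.5 | 144 − 12.5 = 131.5 | 11.5 | 85.6% |

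A single covariate does not achieve this. Under the plan's assumptions the slope on relative boot time is 10 lb in controls and 0 in the intervention arm, so the common fitted slope is about 5. The residual variance is then 144 − 100c² + 25c² in controls and 144 + 25c² in the intervention arm, which averages 144 − 25c²: 141.75 at c = 0.3 and 137.75 at c = 0.5. That is a reduction of 1.6% to 4.3%, and estimating the slope gives some of it back. Simulated power with boot time known perfectly:

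| c | Without covariate | With covariate |
|---|---|---|
| 0.3 | 82.9% | 82.4% |
| 0.5 | 82.7% | 82.4% |

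There is no gain. A clinician's forecast, being less accurate, would not be expected to do better.

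**5. Systematic difference.** If mean boot time differed by arm by 20% or 30% with no treatment effect, the false difference would be 2 or 3 lb, and the test at SD 12 would reject in 8.9% or 13.9% of trials. This does matter, but it arises after randomization, and a baseline forecast of boot time cannot correct it.

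**The case for a change.** The strongest case for a change has four parts.

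- **Drift by arm.** The trial is unblinded, the final weight has no fixed time, and data collection stops at withdrawal (section 3.3.2), so nothing prevents boot time from differing by arm. That is true. But nothing in the protocol suggests how nutrition and seated-exercise information would alter when a foot boot comes off. Section 7.2.2 makes the last visit a standard-of-care visit, and section 4.1 says participants receive the same care as patients outside the study. The risk is a possibility without a stated mechanism, and the covariate would not remove it.
- **The SD may be too small.** Section 9.1 gives no source for the 12 lb. If it left out boot-time variation, power at c = 0.5 would be 79.1% with the spread in controls only, or 76.0% with it in both arms. That reading goes against section 9.1, which defines the SD up to boot removal.
- **Both arms may gain with time.** The covariate would then help: power with a residual SD of √(144 − (10c)²) in both arms is 83.9% at c = 0.25 and 88.8% at c = 0.5. This departs from the plan's expectation of no change in the intervention arm, and most of the gain needs an accurate forecast.
- **Interpretation.** An average change over a treatment period of unstated length (objective 2 in section 1.1) is hard to carry to another clinic. This stands as a point about reporting. Pounds per week is a poor answer to it, because it divides by a quantity observed after randomization and assumes steady gain, which no data in the protocol support.

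**Conclusion.** No change to the plan follows. Total weight change over the boot episode is a legitimate endpoint and matches objective 2. The randomized comparison keeps its error rate of about 5% as long as boot time has the same distribution in both arms, and the stated 82% power holds on the natural reading of the 12 lb SD. Modelling expected boot time leaves power at about 82% under the plan's own assumptions.

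The numerical ranges rest on assumed boot-time CVs and proportional gain, since the documents give neither. The conclusion on validity needs only randomization and no systematic difference in boot time by arm.

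What is missing is a descriptive summary. Enrollment and final visit approximately bracket boot wear, so an analyst can derive boot days from the visit dates and show them by arm, with any duration-based analysis labelled exploratory. That would also show a difference in timing between the arms if one arose. It is ordinary reporting and needs no amendment.

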1.3 Secondary Study Endpoints

1. Pre- and post-albumin levels (to measure protein and provide nutritional status)

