7.2 Study Procedures

7.2.1 Visit 1 - Enrollment

Patients will be given information about the study and asked to participate. If eligible, based on inclusion and exclusion criteria, informed consent will be obtained at the time of the screening visit and the patient will be enrolled in the study.

After obtaining informed consent, patients will be randomized to one of two groups. A sealed envelope will be drawn containing one of the two treatment groups. This study will not be blinded as patients would easily be able to detect which treatment group they are randomized too.

- **Group 1 (Control)** – Patients are prescribed CAM boot as part of their standard of care treatment. No nutritional and exercise information will be provided.

Patients will be given an Albumin lab test request for blood (8mL) to be drawn at the PSHMC Clinical Laboratories at time of enrollment (+/5 days) and again at their final visit (+/- 5 days). Patients with abnormal lab testing results will be referred to their primary care physician for further evaluation and management.

Patient's height and weight will be measured and recorded using a scale already located in the practice site clinic.

- **Group 2 (Intervention)** – Patients are prescribed CAM boot as part of their standard of care treatment and provided nutritional/exercise information at the time the CAM boot is dispensed.

Patients will be provided upper body physical exercises consisting of seated upper body physical exercises (with or without weights) to include chest press, chest pulls, butterfly wings, front raise, upright row, biceps curls, overhead press and triceps extension exercises (Appendix 1). Patient is instructed to perform these exercises three days per week and each exercise three times per session (or to the best of his/her ability).

Patients will be provided nutritional guidelines (Appendix 2) which is intended as a guide for adults who want to follow a healthful eating pattern.

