Patients will also be given a Patient Diary (Appendix 3) to complete their daily meal intake and physical exercises. Use of and return of the diary is optional but encouraged. A dietary scale will also be provided for use throughout the study for weighing food if participants are interested. This is also an optional component of the study. It has been found that use of a patient diary to record food intake and a dietary scale to weigh food helps teach portion control and keeps one from eating more than they planned. They can be useful tools in weight control.

Patients will also be given an Albumin lab test request for blood (8mL) to be drawn at the PSHMC Clinical Laboratories at time of enrollment (+/- 5 days) and again at their final visit (+/- 5 days). Patients with abnormal lab testing results will be referred to their primary care physician for further evaluation and management.

Patient's height and weight will be measured and recorded using a scale already located in the practice site clinic.

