9.2 Statistical methods

Baseline characteristics between the two groups (CAM boot + no nutritional information and CAM boot + nutritional information) will be compared using a chi-square test for categorical variables (e.g., sex) and a two-sample t-test for continuous variables (e.g., the primary of the change in weight from baseline to

CAM boot removal). In the event a continuous outcome is not normally distributed, the nonparametric Wilcoxon Mann Whitney test will be used rather the two-sample t-test.

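### Albumin, the only secondary endpoint, has no stated summary measure and only unadjusted tests; comparing final albumin adjusted for enrolment albumin would generally be more precise

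*Combined protocol and SAP*

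**What the plan says.** Section 1.3 lists one secondary endpoint: "Pre- and post-albumin levels (to measure protein and provide nutritional status". It names two measurements but no quantity to compare between arms.

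Both arms give both samples. Section 7.2.1 says, for the control arm, "Patients will be given an Albumin lab test request for blood (8mL) to be drawn at the PSHMC Clinical Laboratories at time of enrollment", and gives the intervention arm the same request. Section 7.2.2 repeats it for both arms at the last visit: "Patient will be given an Albumin lab test request for blood (8mL) to be drawn at the PSHMC Clinical Laboratories at time of the final". The window stated for the intervention arm is "at time of enrollment (+/- 5 days) and again at their final visit (+/- 5 days".

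Section 9.2 is the whole analysis plan. For continuous data it names "a two-sample t-test for continuous variables (e.g., the primary of the change in weight from baseline to", where the example is weight change up to removal of the boot. If the outcome is not normally distributed, "the nonparametric Wilcoxon Mann Whitney test will be used rather the two-sample t-test". It mentions no albumin analysis, covariate or regression. Weight is handled differently: 9.1 and 9.2 both treat it as a change from baseline.

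**The concern.** The plan leaves open which albumin number enters the test, and none of its tests adjusts for the enrolment value. Two choices are natural. Comparing final levels leaves the enrolment draw unused. Comparing changes uses both draws but gives the enrolment value a fixed weight of one, which over-corrects when the draws are only moderately correlated. A regression of final albumin on arm and enrolment albumin estimates that weight from the data.

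Precision on the only secondary endpoint is at stake, in a trial with 25 patients per arm whose blood is drawn twice for this purpose. There is also a choice to be fixed in advance: a final-level test, a change test and an adjusted comparison can give different answers from the same data, and section 7.2.1 states that the trial is not blinded.

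**Working it through.** **The plan's own figure.** Section 9.1 states that "a sample size of 25 per group will provide 82% power to detect a difference in the change in weight between the two groups" for a 10 lb difference, SD 12 lb, two-sided 0.05. The noncentrality is 10 / (12 × √(2/25)) = 2.946. The noncentral t with 48 degrees of freedom gives 82.3%, and the normal approximation 83.8%. The stated 82% reproduces. No such figure is given for albumin.

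**Inputs for albumin.** There are 25 patients per arm (9.1) and two draws per patient (7.2.1, 7.2.2). The documents give no albumin SD and no correlation r between the draws. I assume equal SDs at the two draws and let r range from 0 to 0.9.

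**Formulas.** Variance of the arm difference, relative to comparing final levels alone:

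- final level: 1
- change from enrolment: 1 + 1 − 2r = 2(1 − r)
- final level adjusted for enrolment level: 1 − r²

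Hence adjusted ÷ change = (1 − r²) / [2(1 − r)] = (1 + r)/2, and adjusted ÷ final = 1 − r².

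**Results.** Large-sample ratios, with simulated values at 25 per arm (20,000 runs for each r) in brackets:

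| r | change | adjusted | adjusted ÷ change | adjusted ÷ final |
|---|---|---|---|---|
| 0.3 | 1.40 | 0.91 | 0.65 (0.67) | 0.91 (0.93) |
| 0.5 | 1.00 | 0.75 | 0.75 (0.76) | 0.75 (0.77) |
| 0.7 | 0.60 | 0.51 | 0.85 (0.87) | 0.51 (0.53) |
| 0.8 | 0.40 | 0.36 | 0.90 (0.92) | 0.36 (0.37) |
| 0.9 | 0.20 | 0.19 | 0.95 (0.97) | 0.19 (0.20) |

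At r = 0 and r = 0.1 the simulated adjusted ÷ final ratio is 1.02, so adjustment is then about 2% worse than the final level alone.

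**On the scale of the interval.** Width follows the square root of the variance. At r = 0.5, √0.75 = 0.866, about 13% narrower than with either alternative. Against a change score, the narrowing is about 8% at r = 0.7 (√0.85 = 0.922) and about 3% at r = 0.9 (√0.95 = 0.975).

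**On the scale of power.** These figures use 47 degrees of freedom and a small-sample variance inflation of 47/46. If a change-score test had 80% power, the adjusted analysis would have about 93%, 89%, 85%, 83% and 81% at r = 0.3, 0.5, 0.7, 0.8 and 0.9. If a final-level test had 80%, the adjusted analysis would have about 79%, 83%, 89% and 97% at r = 0, 0.3, 0.5 and 0.7.

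**The case against.** A reader might infer that, because each test in 9.2 takes one value per patient, much of the information in the enrolment draw is wasted. The documents do not support that. A change from enrolment is one value per patient and uses both draws, and it is the form 9.2 gives for weight, the only continuous outcome it names. On that reading the loss is 10% of variance at r = 0.8 and 5% at r = 0.9. The large losses arise only if final levels alone are compared and r is high. No text says that this will be done, or that enrolment albumin will be tested between arms, although 9.2 opens with the comparison of baseline characteristics.

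A reader might also infer that adjustment is free. It is not:

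- It spends a degree of freedom and assumes linearity.
- A complete-case fit drops patients who lack an enrolment draw, whom a final-level comparison would keep.
- The enrolment value may not be a clean baseline. Section 7.2.1 places randomisation, the materials and the laboratory request at the same visit and allows the draw a 5-day window, so it can follow both randomisation and receipt of the materials.

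Finally, the objectives, hypotheses and power calculation concern weight only, so albumin is supportive and unpowered.

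All of this limits the size of the point and shapes the remedy. It does not remove the point. The plan does not choose between level and change, section 2.2 reports no previous data from which r could be judged, and the adjusted analysis does well across the range without r being known.

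**Conclusion.** The point holds as a modest gain in precision. The albumin comparison is undefined, and either natural way of completing it under 9.2 is valid but generally less precise than a baseline-adjusted comparison of the same two draws. How much less depends on an unstated correlation and an unstated choice of measure: between 5% and 35% of variance against a change score, and between 9% and 81% against the final level, for r from 0.3 to 0.9 with equal SDs. With r near 0, adjustment loses about 2% against the final level. The primary weight analysis and the sample size are not affected.

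**What to change.** In 1.3, define the endpoint as the between-arm difference in final albumin. In 9.2, add wording such as: *Final albumin will be compared between randomised arms by linear regression with enrolment albumin as covariate, reporting the adjusted mean difference and its 95% confidence interval. Enrolment and final levels will be summarised descriptively by arm; enrolment albumin will not be tested between arms.*

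Two safeguards belong with it:

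- **Timing.** Record the date of the enrolment draw. Treat the value as baseline only if the draw came before the intervention materials were given; otherwise show a sensitivity analysis that excludes later draws.
- **Missing enrolment draw.** Keep patients who lack only this value by a simple baseline imputation, for example the mean enrolment value over both arms combined, so that the regression does not lose them.

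The cost is a few sentences and one recorded date, with no new visits or blood draws. The statistical price is one degree of freedom, a linearity assumption, and about 2% of variance against the final level if the two draws turn out to be almost uncorrelated.

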2.0 Background

2.1 Scientific Background and Gaps

There does not appear to be any literature related to this topic. The potential value in completing this study is to provide a better understanding to the health care provider of the necessity to provide information regarding weight maintenance information to the patient when they are placed in a CAM boot for a foot pathology, thereby reducing the risk of weight gain in a CAM boot.

2.2 Previous Data – N/A

2.3 Study Rationale

We hypothesize that participants who are provided nutritional and gender appropriate upper body exercise information, at time CAM boot is prescribed, will maintain their current weight or lose while in the CAM boot. We further hypothesize that participants without nutritional and gender appropriate upper body exercise will gain between 10-15 pounds on average.

3.0 Inclusion and Exclusion Criteria

3.1 Inclusion Criteria

- Participants \geq 18 years of age
- Sex: male or female
- Participants prescribed a CAM boot as standard of care from the principal investigator's practice
- Participants willing to have weight measured at the clinic site at time of enrollment and at final visit
- Participants willing to have blood drawn for Albumin level at beginning and end of study
- Participant is able to provide voluntary, written informed consent
- Participant, in the opinion of the clinical investigator, is able to understand the clinical investigation and is willing to perform all study procedures and follow-up visits.
- Fluent in written and spoken English

